### **Statistical Analysis:**

Patient characteristics, objective measurements and patient questionnaires will be summarized using descriptive statistics such as mean with standard deviation and mean or frequency with percentage. Comparisons of outcomes measured between baseline and postop will be assessed using the paired t-test or McNemar's test. A total of 26 patients is required to achieve 80% power for a paired t-test with a significance level of  $\alpha=0.05$  and a moderate effect size of  $d=0.50$ . All statistical analysis will be performed using SAS 9.4 (SAS Institute, Cary, NC) with two-sided tests and  $p<0.05$  considered statistically significant.

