## **RESEARCH DESIGN AND METHODS**

### **Study Design:**

This is a prospective, non-randomized trial to assess objective improvement in nasal patency after undergoing treatment of the nasal valve with VivAer. Up to twenty-six subjects will be enrolled in this trial. Patients presenting with nasal obstruction and no notable septal deviation will be instructed to complete four weeks of intranasal steroid sprays. After patients complete the intranasal steroid spray, they will return to the clinic to assess nasal patency. If nasal obstruction symptoms persist, their eligibility for the VivAer procedure is assessed. The inclusion and exclusion criteria outlined below will be reviewed. If the patient is eligible and interested in receiving the VivAer procedure, they will be consented and receive a date to undergo the procedure. At the procedure date, they will perform baseline peak nasal inspiratory flow (PNIF) measurements and complete baseline Sino-Nasal Outcome Test (SNOT-22) scores and Nasal Obstructive Symptom Evaluation (NOSE) scores. After the procedure, subjects will be off steroid sprays for 2 weeks and will only use nasal saline irrigations during the procedure-recovery period. Subjects will return to clinic for evaluation at 4 weeks, 12 weeks and 24 weeks post procedure and during each of these visits will complete interval PNIF measurements, SNOT-22 scores, and NOSE scores.

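### The stated 80% power with 26 patients does not hold for the two-sided paired t-test the plan specifies: 26 complete pairs give 69%, and enrolment stops at 26 with no allowance for loss

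*Combined protocol and SAP*

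**What the plan says.** The only justification of the study's size is one sentence in the Statistical Analysis section: "A total of 26 patients is required to achieve 80% power for a paired t-test with a significance level of" 0.05 and a moderate effect of d = 0.50. It names no outcome and does not say which standard deviation scales d.

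The sentence before it gives the method: "Comparisons of outcomes measured between baseline and postop will be assessed using the paired t-test or McNemar's test". The sentence after it fixes the sidedness: "All statistical analysis will be performed using SAS 9.4 (SAS Institute, Cary, NC) with two-sided tests and" sets the threshold at p < 0.05.

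Study Design sets the enrolment limit: "Up to twenty-six subjects will be enrolled in this trial". The same section gives the follow-up: "Subjects will return to clinic for evaluation at 4 weeks, 12 weeks and 24 weeks post procedure". Neither section gives an expected rate of loss or adds patients to cover it.

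**The concern.** A paired t-test with d = 0.50, a two-sided 5% level and 80% power needs clearly more than 26 pairs, so the sample-size sentence and the two-sided rule in the same paragraph do not fit together. In addition, a power calculation for a paired test counts patients with both measurements. Here the required number equals the enrolment ceiling, so each patient without a follow-up value lowers the power further.

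At stake is what a non-significant result would mean. The introduction says the earlier favourable results rest on patient symptom scores, and it proposes objective measurement of airflow as the purpose of this study. If the true PNIF effect is near the planned size, the study misses it more often than the plan states. A reader who trusts the stated 80% would give a negative PNIF result more weight than it deserves.

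**Working it through.** **Inputs.** From Statistical Analysis: paired t-test, α = 0.05, two-sided, d = 0.50, n = 26, stated power 80%. From Study Design: at most 26 enrolled. Assumption: d is the mean change divided by the SD of the change, the usual meaning for a paired t-test. The plan gives no SD and no within-patient correlation.

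**Method.** The paired t statistic follows a noncentral t distribution with n − 1 degrees of freedom and noncentrality d√n. Two-sided power is P(T > t₀.₉₇₅,ₙ₋₁) + P(T < −t₀.₉₇₅,ₙ₋₁). One-sided power is P(T > t₀.₉₅,ₙ₋₁).

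**1. Reproducing the plan's figure.** For n = 26 the noncentrality is 0.50 × √26 = 2.550 on 25 degrees of freedom.

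| Test at 5% | Critical value | Power at n = 26 | n for 80% |
|---|---|---|---|
| One-sided | 1.708 | 79.8% | 27 (81.2%) |
| Two-sided, as the plan specifies | 2.060 | 68.8% | 34 (80.8%) |

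At n = 33 the two-sided power is 79.5%, just short. The stated 26 is recovered, within rounding, only with a one-sided test. That this is where it came from is an inference; the two-sided shortfall does not depend on it.

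**2. Normal approximation as a check.** n = ((z_α + z_power)/d)².

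- Two-sided: ((1.960 + 0.842)/0.5)² = 31.4, so 32 pairs.
- One-sided: ((1.645 + 0.842)/0.5)² = 24.7, so 25 pairs.

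The approximation does not account for the gap: two-sided, it gives 72.2% power at 26 pairs.

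**3. Loss to follow-up.** The plan gives no rate, so these rates are assumptions, applied to 26 enrolled.

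| Assumed loss | Complete pairs | Two-sided power at d = 0.50 | Enrolment for 34 completers |
|---|---|---|---|
| 0% | 26 | 68.8% | 34 |
| 5% | 25 | 67.0% | 36 |
| 10% | 23 | 63.0% | 38 |
| 15% | 22 | 60.9% | 40 |
| 20% | 21 | 58.7% | 43 |

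The last column is 34/(1 − loss), rounded up; for example, 34/0.90 = 37.8, so 38.

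**4. Effect detectable with 80% power, two-sided.** d = 0.57 with 26 pairs, 0.61 with 23 and 0.64 with 21.

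**5. The other meaning of d.** If d = 0.50 is scaled by the SD at a single time point, with equal SDs and baseline to follow-up correlation r, the effect on the scale of the change is 0.50/√(2(1 − r)). With 26 pairs this must reach 0.572, so r = 1 − (0.50/0.572)²/2 ≈ 0.62. Two-sided power at 26 pairs is 68.8% for r = 0.5, 78.2% for r = 0.6 and 88.5% for r = 0.7.

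**The case against.** There are four main points on the other side.

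**The definition of d is open.** If d is scaled by the single-occasion SD, any correlation of about 0.62 or more brings 26 pairs to at least 80%. That is a range of values, not one lucky value. This stands as a possibility, but the plan states neither the scaling nor a correlation. On that reading the sentence would still lack the assumption on which its power depends.

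**The consequence depends on the true effect.** The 31% risk applies only at d = 0.50. With 26 pairs, power is 84% at d = 0.60 and 97% at d = 0.80. For NOSE the effect is probably much larger. Entry requires a score of at least 60 and the introduction cites a 67% reduction, so a drop of about 0.67 × 60 = 40 points; d = 0.50 would then need an SD of change near 40/0.50 = 80 points. This stands: the shortfall is unlikely to matter for NOSE. It does not cover PNIF, for which no expected effect or SD is given.

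**No passage says how a negative result would be read.** This is true, so over-reading a negative PNIF result is a risk and not something the plan commits to. Nor does the error inflate the false-positive rate or bias an estimate.

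**The study is small, open-label and single-arm, with no stated success rule.** That bears on how serious the error is. It does not make the stated power correct.

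**Conclusion.** The concern holds. For the two-sided paired t-test at 5% that the plan specifies, 26 complete pairs have 68.8% power at d = 0.50, not 80%, and 80% needs 34 complete pairs. The chance of missing an effect of that size is 31% rather than 20% before any loss. With an assumed 10% to 20% loss from the ceiling of 26, power falls to between 63.0% and 58.7%.

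The conclusion rests on d being the mean change over the SD of the change. The only reading that keeps 80% with two-sided tests requires a correlation of about 0.62 or higher, which the plan does not state. The practical effect is confined to outcomes whose true effect is near 0.50; PNIF may be one of them. The sentence needs correction because it is the study's only size justification and disagrees with the two-sided rule beside it.

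**What to change.** Replace the power sentence with wording such as: With 26 evaluable patients, a two-sided paired t-test at the 0.05 level has 69% power for d = 0.50 and 80% power for d = 0.57, where d is the mean change divided by the SD of the change. Name the outcome to which this applies, and add the power at the expected number of completers, with the assumed loss stated. If d was meant on the single-occasion SD, state the assumed correlation and its basis.

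This needs no extra patients; the cost is a less favourable stated power. If the investigators want to keep 80% at d = 0.50, the alternative is to raise the ceiling so that 34 patients complete, for example 38 enrolled at an assumed 10% loss.

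As an optional addition, a repeated-measures mixed model over all visits, a standard analysis in SAS, would let a patient who misses the final visit still contribute through earlier follow-up values. It adds little for a patient with no post-procedure value, no power has been calculated for it here, and it does not replace the corrected sentence.

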## **FORESEEABLE RISKS AND DISCOMFORTS**

Discomfort that is expected in the treatment area rarely will include inflammation/redness, swelling/edema, blanching, numbness, bruising, soreness/pain, bleeding at local anesthetic injection site, bleeding at the treatment site, nasal obstruction from tissue edema, disruption of mucosal flow/crusting.

Potential risks that have not been reported with VivAer but are theoretical risks after this treatment include the following: infection, bleeding greater than anticipated by the investigator, scar formation with subsequent nasal obstruction, sensory changes at the treatment site.

## **EXPECTED BENEFITS**

It is anticipated that this procedure will improve nasal breathing. VivAer is minimally invasive. The objective data received from this study will help clinicians provide better guidance to patients interested in receiving this treatment.

## **EQUITABLE SELECTION OF SUBJECTS**

Patients will not be categorically excluded from this research. The study population will be limited to those who are eligible based on the inclusion criteria for this study. If an eligible patient speaks another language aside from English, the study team will follow the institutions short form consent process. This will ensure all patients have the equitable right to participate in this research, while maintaining their comprehension of the study.

## **RECRUITMENT PROCEDURES**

Physician's practices will be the basis of recruitment for this clinical trial.

## **CONSENT PROCEDURES**

All subjects will receive the consent form for the study. This document will be read by the patients and reviewed by the patient with a licensed physician investigator and/or research study staff prior to participating in the study. The patient will be given as much time as they need to review the consent. [name] MD, [name] MD, or another licensed physician investigator will clarify any questions, concerns, or ambiguities prior to the patient signing consent. Patients will sign informed consent and only then will begin participation in the study. If new information is ascertained during the study, we will modify our consent and re-consent our patients.

## **DATA AND SAFETY MONITORING**

Each site will conduct weekly research meetings with co-investigators and study staff to review study progress, including recruitment strategies, enrollment numbers, protocol issues, and safety issues. The PIs will participate in monthly conference calls regarding study progress.

Documentation of the presence of any side effect or adverse event will be completed at every visit using the adverse event classification available in appendix 1. Patients will be asked to contact an investigator or study staff member at any time concerning adverse events or worsening symptoms. All treatment related Serious Adverse Events (SAE) will be documented and reported immediately to the NorthShore IRB in line with institutional and regulatory requirements. In the event that a patient becomes ill or injured as a direct result of participation in the research study, necessary medical care will be available. All SAEs will be followed to resolution or stabilization.

## **MONITORING AND QUALITY ASSURANCE**

[name] and [name] will oversee and monitor the study at an ongoing basis to ensure that it is being executed accurately and per protocol. Both will be responsible for monitoring the data collected, and the reporting of study-related adverse events to the IRB in accordance with adverse event reporting policies.

## **PRIVACY AND CONFIDENTIALITY**

Medical information produced by this study will be stored in the investigator's file and identified by code number only. The code key connecting a specific name to specific information will be kept in a separate, secure location. Information contained in the records will not be given to anyone unaffiliated with NorthShore in a form that could identify the subject without the subjects written consent, except as described in the consent form or as required by law. It is possible that medical and research records, including sensitive information and/or identifying information, may be inspected and/or copied by federal or state government agencies, or hospital accrediting agencies, in the course of carrying out their duties. However, they are required to maintain confidentiality in accordance with laws and policies of the Hospital.

**Appendices:**

**Appendix 1:**

**Adverse Events Definitions**

**1. Adverse Event (AE)**

- a. Any untoward medical occurrence, unintended disease or injury or any untoward clinical signs (including an abnormal laboratory finding) in subjects, users or other persons whether or not related to the investigational medical device.

**2. Serious Adverse Event (SAE): any AE that**

- a. Led to death, or
- b. Led to serious deterioration in the health of the subject, that either:
  - i. Resulted in a life-threatening illness or injury, or
  - ii. Resulted in a permanent impairment of a body structure or a body function, or
  - iii. Required in-patient or prolonged hospitalization, or
  - iv. Resulted in medical or surgical intervention to prevent life-threatening illness or injury or permanent impairment to a body structure or a body function, or
- c. Led to fetal distress, fetal death, or a congenital abnormality or birth defect.

**3. Unanticipated Adverse Device Effect (UADE)**

- a. *Unanticipated adverse device effect* means any serious adverse effect on health or safety or any life-threatening problem or death caused by, or associated with, a device, if that effect, problem, or death was not previously identified in nature, severity, or degree of incidence in the investigational plan or application (including a supplementary plan or application), or any other unanticipated serious problem associated with a device that relates to the rights, safety, or welfare of subjects.

## VIVAER: CORRELATION OF SYMPTOMS & FINDINGS

### 4. Severity

- a. The Investigator or designee is required to determine severity of the AEs reported. The following definitions are used for determination:

**Mild** – Easily tolerated by the subject, causing minimal discomfort and not interfering with everyday activities. These events generally do not require treatment.

**Moderate** – Sufficiently discomforting to interfere with normal everyday activities. These events are usually relieved by simple therapeutic measures.

**Severe** – Prevents normal, everyday activities. These events may require systemic drug therapy, other medical treatment, or return to the operating room.

### 5. Relationship to Investigational Device

- a. The Investigator or designee is required to determine the relationship of each AE to the investigational device. The following definitions are used for determination:

- i. **Definite** – The AE follows a known or expected response pattern to the device and the physician confirms the relationship through further testing or evidence.
- ii. **Probable** – The AE follows a known or expected response pattern to the device.
- iii. **Possible** – The AE follows a known or expected response pattern to the device but could readily have been produced by a number of other factors.
- iv. **None** – An AE for which sufficient information exists to indicate that the etiology is unrelated to the device; the AE is readily explained by the subject's clinical state or other therapies.
